2. STUDY OBJECTIVES

Primary and secondary objectives

The primary objective of this study is to compare the efficacy of gabapentin enacarbil 600 mg BID taken 1 day pre-op and approximately 2 hours before the surgery and restarted within 6 hours of completion of surgery and then 3 days post-operative versus placebo in reducing the use of opiates and/or pain scores in post-hip and knee arthroplasty surgery patients with spinal anesthesia.

Using a randomized design and blinded assessments, our goal is to determine whether Gabapentin enacarbil when used as a modality of pre-emptive analgesia decreased opioid consumption and/or decreased pain scores in hip and knee arthroplasty surgery.

The proposed research will have the following aims:

Primary objectives include:

Primary Aim 1: To assess whether gabapentin enacarbil decreases pain and/or opioid requirements after hip or knee surgery.

Hypothesis: Patients received gabapentin enacarbil will have less pain scores and/or less opioid consumption during the initial 72 hours after hip or knee surgery compared to patients who received placebo, and not worse on either outcome.

Secondary objectives include:

Secondary Aim 1: To assess whether gabapentin enacarbil decreases the incidence of persistent incisional pain three months after surgery when used as a modality of pre-emptive analgesia.

Hypothesis: Gabapentin enacarbil decreases the persistence of incisional pain three months after surgery.

Secondary Aim 2: To evaluate whether gabapentin enacarbil decreases nausea and vomiting during the initial 72 post-operative hours.

Hypothesis: The incidence of postoperative nausea and vomiting is reduced in patients given gabapentin enacarbil during the initial 72 hours after hip and knee replacement surgery.

Secondary Aim 3: To evaluate whether gabapentin enacarbil reduces the duration of hospitalization.

Hypothesis: The duration of hospitalization after knee or hip arthroplasties is reduced in patients given gabapentin enacarbil.

Secondary Aim 4: To evaluate whether gabapentin enacarbil will improve patient's satisfaction.

Hypothesis: Patients are more satisfied with the pain and quality of life after taking gabapentin enacarbil compared to placebo, as assessed using the quality of recovery score (QoR-15).

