3.2 Primary Study Endpoints

To assess whether gabapentin enacarbil improves quality of postoperative analgesia characterized by decreased pain and/or opioid requirements after hip or knee surgery. Cumulative opioid consumption in the PACU and floor for the first 72 hours after surgery or till discharge whichever comes first. The total dose of opioid administered includes the background analgesia provided by morphine PCA, fentanyl PCA or hydromorphone PCA, rescue doses of IV fentanyl, IV

hydromorphone, and PO oxycodone. All opioids will be converted into morphine equivalents to standardize opioid consumption (10 mg of IV morphine = 100 mcg of IV fentanyl = 1.5 mg of IV hydromorphone = 20 mg of PO oxycodone) the total number of requested PCA boluses will also be recorded, along with the number of requests that were actually delivered.

Postoperative pain intensity will be evaluated in the PACU using a 0-10 Numeric Rating Scale (NRS), where 0 is no pain and 10 is the worst possible pain. Pain will be assessed every 15 min for the first one hour after surgery and then every morning for three post-operative days as long as the patients are hospitalized.

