4. SUBJECT SELECTION AND WITHDRAWAL

4.1 Inclusion Criteria

To be eligible for entry into this study, candidates must meet all of the following eligibility criteria at the time of randomization:

1. Men or women 18-85 years of age.
2. Scheduled for elective knee or hip arthroplasty with spinal anesthesia.

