4.2 Exclusion Criteria

Candidates will be excluded from study entry if any of the following exclusion criteria exist at the time of randomization.

1. Creatinine >1.50 mg/dl.
2. History of clinically important current depression or currently on any prescribed anti-depressant medication.
3. Previously enrolled in any Xenoport trial.
4. Use of gabapentin or gabapentinoids (Lyrica, Horizant, Neurontin or Gralise) within one month.
5. Allergy to gabapentin or gabapentinoids (Lyrica, Horizant, Neurontin or Gralise).
6. Women who are pregnant or breastfeeding.

7. History of seizure disorder within the last one-year or taking medications for seizures.

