5.3 Method for Assigning Subjects to Treatment Regimen

Participating patients will be randomly assigned to gabapentin enacarbil or placebo. Randomization will be web-based through REDCap and stratified by type of surgery. Allocation will be concealed until shortly before drug/placebo administration. Randomization will be stratified by type of surgery (hip versus knee). Randomization codes will be web based using random-sized blocks, and treatment assignment (gabapentin enacarbil or placebo) will be done using a password-protected website administered by the Department of Outcomes Research statistical team at Cleveland Clinic.

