5.6 Prior and Concomitant Therapy

Patient will not receive any gabapentinoids from the start of study drug to the end of postoperative 72 hours period. All other pain medications will be allowed.

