⁵ Physical evaluations include monitoring vital signs, checking general wellbeing and pain evaluation both pre-operatively and post-operatively. Patients will be evaluated by orthopedic surgeons pre-operatively and post-operatively as per their protocol. Physical therapy will evaluate the patients for pain, mobility and strength as per physical therapy protocol. Physical therapy and orthopedic surgeons will record and document their findings in EPIC.

⁶ Patients will be monitored throughout their stay in the hospital and will be asked to report any adverse event or any untoward event to the research fellow. Patients will be also be inquired for any side effects during the phone call made 3 months after surgery.

⁷ Data will be collected through personal interview and through electronic medical records. Data will also be collected through the phone call made 3 months after surgery.

Pre-operative data collection:

1. Pain scores using numerical rating scores (NRS) during the pre-operative evaluation visit
2. Brief pain inventory (BPI) at pre-operative evaluation visit.
3. Demographic data to be obtained includes height (cm), weight (kg), age (yr.), gender, (ASA) physical status, and self-declared ethnicity.
4. Patients will be questioned for social history (tobacco) and medical history (pulmonary disease, kidney disease, diabetes mellitus, neurological disease, chronic pain conditions, illegal drug usage, alcohol abuse, myocardial infarction, previous surgery or stent placement and medications usage).
5. Available preoperative laboratory tests and medication list will be recorded.
6. Individual risk for nausea and vomiting will be determined using the Apfel score.

Post-operative data collection:

1. Pain scores using numerical rating scores (NRS):
 - a. Every 15 minutes for the first hour after surgery.
 - b. Every four hours after the first hour until 72 hours after the surgery.
2. Brief pain inventory (BPI) prior to hospital discharge or at 72 hours post op whichever comes first
3. The QoR-15 score to formally evaluate quality of recovery. The QoR-15 score is a validated scoring system allows quantification of patient's early postoperative health status, which is also a description of quality of recovery. The QoR-15 scoring will be done prior to hospital discharge or at 72 hours post op whichever comes first.

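### Pre-operative opioid use can be derived from data already recorded but is neither a stratum nor a covariate, and the plan does not say whether continued home opioid counts in the co-primary total

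*Combined protocol and SAP*

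**What the plan says.** **Eligibility.** Section 4.1 requires age 18-85 and "Scheduled for elective knee or hip arthroplasty with spinal anesthesia". Section 4.2 has seven exclusions. The one on analgesic use is "Use of gabapentin or gabapentinoids (Lyrica, Horizant, Neurontin or Gralise) within one month"; none concerns prior or chronic opioid use.

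**Concomitant drugs.** Section 5.6 bars gabapentinoids through 72 hours after surgery and then says "All other pain medications will be allowed".

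**Outcome.** Section 3.2 defines "Cumulative opioid consumption in the PACU and floor for the first 72 hours after surgery or till discharge whichever comes first". It lists PCA opioid and rescue doses of IV fentanyl, IV hydromorphone and oral oxycodone, and then states "All opioids will be converted into morphine equivalents to standardize opioid consumption". Home opioid is not mentioned, either as included or as excluded.

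**Randomisation.** Section 5.3: "Randomization will be stratified by type of surgery (hip versus knee)". No other factor is named.

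**Analysis.** Section 7.2 compares the arms with a log-linear model for opioid dose and a linear model for the time-weighted average (TWA) pain score. No covariate is named for either, not even the hip/knee stratum. Baseline variables are compared descriptively, with no rule for what follows from an imbalance.

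**Data at hand.** Section 6.4, footnote 7: "Available preoperative laboratory tests and medication list will be recorded". The same footnote collects medication use and chronic pain conditions.

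**The concern.** The hypothesis in section 2 is "Patients received gabapentin enacarbil will have less pain scores and/or less opioid consumption during the initial 72 hours after hip or knee surgery". A patient who came to surgery already taking an opioid may have a higher 72-hour total for reasons unrelated to the operation or the study drug. Two things follow.

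First, prior opioid use is a plausible strong predictor of the outcome. Left out of the model, it stays in the residual variance of an analysis whose sample size is fixed at 100.

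Second, the endpoint definition is incomplete. Oral oxycodone on the floor could be rescue or a continued home dose, and drug and route alone do not tell them apart. If a home dose is counted and treatment does not change it, it adds the same amount in both arms and pulls the ratio of geometric means toward 1.

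The opioid outcome carries one of the two noninferiority tests (ratio margin 1.1) and one of the two superiority tests, so its precision bears directly on the primary claim.

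**Working it through.** **Inputs from the plan (sections 7.1 and 7.2).** 50 per arm; CV 0.7 in both groups; ratio of geometric means 0.63; one-sided level 0.0125; stated power about 90%.

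**1. The plan's own figure.**
- Log-scale variance = ln(1 + 0.7²) = ln(1.49) = 0.399, so the log-scale SD is 0.631.
- Effect = ln(0.63) = −0.462.
- Standard error of the log ratio = 0.631 × √(2/50) = 0.126.
- Noncentrality = 0.462 / 0.126 = 3.66. With a one-sided t-test on 98 degrees of freedom, power is 91.5%.

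This reproduces the stated figure, which is not in dispute.

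**2. Variance carried by opioid users.** The documents give neither the share of users, p, nor the ratio k of their 72-hour total to that of other patients. Both are assumptions here: p = 10% or 20%, k = 2. A yes/no factor contributes p(1 − p)(ln k)² to the log-scale variance, with (ln 2)² = 0.480.
- p = 0.10: 0.09 × 0.480 = 0.043.
- p = 0.20: 0.16 × 0.480 = 0.077.

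The plan gives no source for the CV of 0.7, so both readings are shown.

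| Reading | p | Log variance | Log SD | Power at 0.63 |
|---|---|---|---|---|
| CV 0.7 includes users; model adjusts for the flag | 10% | 0.399 − 0.043 = 0.356 | 0.596 | 94.3% |
| same | 20% | 0.399 − 0.077 = 0.322 | 0.567 | 96.2% |
| CV 0.7 excludes users; model does not adjust | 10% | 0.399 + 0.043 = 0.442 | 0.665 | 88.3% |
| same | 20% | 0.399 + 0.077 = 0.476 | 0.690 | 85.7% |

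On the first reading the unadjusted analysis keeps its 91.5% and adjustment is a gain. On the second, the unadjusted analysis falls short of plan and adjustment recovers the loss.

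**3. Dilution if home opioid is counted.** Step 2 holds the ratio at 0.63 in everyone, so it cannot show dilution. A simulation of the planned unadjusted model (3,000 trials per case) does. It assumes a true ratio of 0.63 on acute opioid only, CV 0.7 for the acute dose, the same acute need in users and non-users, and a fixed home dose stated as a multiple of the control median acute 72-hour dose.

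| Users | Home dose | Estimated ratio | Power unadjusted | Power with yes/no covariate |
|---|---|---|---|---|
| 10% | 0.5 | 0.64 | 89% | 91% |
| 20% | 1 | 0.66 | 78% | 90% |

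The covariate recovers most of the power, but a yes/no flag does not take the home dose out of the total. Only a counting rule does that.

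**4. Chance imbalance.** With 20 users among 100 patients split 50/50, an arm difference of 6 or more users has probability 21% (hypergeometric, either direction). At k = 2 a difference of 6 moves the ratio by 2^(6/50) = 1.087, which is 0.083 on the log scale. That is below one standard error (0.126).

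**The case against.** Four points weigh on the other side.

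**Randomisation already deals with it.** It prevents systematic bias, and the t-test allows for chance imbalance. A reader might infer from step 4 that an imbalance in users could by itself use up the 10% noninferiority margin. That is not supported: the shift is less than one standard error, within the sampling error the confidence interval already covers, and Type I error is unaffected.

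**Home opioid may not be meant to count.** A reader might infer that the plan scores maintenance opioid as postoperative requirement. The components named in section 3.2 are PCA and rescue drugs, and the conversion factors cover only those. The text is silent on home opioid, so the supportable statement is that its handling is unspecified.

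**The medication data are not idle.** They serve eligibility (current antidepressants, seizure medication and recent gabapentinoids are exclusions), and preoperative variables enter the balance comparison. What is missing is a prespecified role for prior opioid use in the primary analysis.

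**A power loss is not shown.** This stands. CV 0.7 may already describe a mixed population, in which case the planned power holds and adjustment only adds to it. Enrolling opioid users and analysing total consumption is also a legitimate pragmatic choice, and the protocol calls the study a pilot.

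What remains is that adjustment improves precision on either reading of the CV if prior use predicts the outcome, and that the endpoint needs a counting rule.

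**Conclusion.** The point holds as an improvement in precision and a clarification of the endpoint; it is not a flaw that threatens validity. Opioid users are eligible, the treatment of their home opioid in the total is unstated, and a probable predictor obtainable from recorded data is left out of both the randomisation and the models.

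Under the assumption of 10-20% users with twice the total, the stake is a rise from 91% to 94-96% power if CV 0.7 includes them, or unadjusted power of 86-88% if it does not. If a home dose is counted, the two simulated cases move the estimated ratio from 0.63 to 0.64 and 0.66. All of these sizes depend on shares and doses that the documents do not give. Severity: consider.

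**What to change.** - **Section 7.2:** prespecify pre-operative opioid use (yes/no, derived from the recorded medication list), together with the existing hip/knee stratum, as covariates in the log-linear opioid model and the TWA pain model.
- **Section 3.2:** state whether continued home opioid is counted in the 72-hour total.
- **Section 7.2:** add one sensitivity analysis of the opioid outcome in patients who were not using opioids before surgery.
- **Optional, section 5.3:** add the flag as a second randomisation stratum (2 × 2 = 4 strata). The covariate delivers most of the benefit without it.

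The cost is a few sentences, slightly more analysis work and one or two degrees of freedom out of 98. Eligibility and care do not change. If enrolment has begun, the covariates, the counting rule and the sensitivity analysis can still be fixed before unblinding; chosen afterwards, they would be post hoc.

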3.3 Secondary Study Endpoints

1. To assess whether gabapentin enacarbil decreases the incidence of persistent incisional pain three months after surgery when used as a modality of pre-emptive analgesia. Patients will be invited to respond at 90 days to questions that are suitable for a telephone interview: any development of new pain or persistence of pain over the surgery site. After 3-months patients will be asked if they experience incisional area pain.
2. To evaluate whether gabapentin enacarbil decreases nausea and vomiting during the initial 72 hours after knee or hip surgery. The incidence of opioid related adverse events e.g. Post-operative nausea and vomiting during the first 72 hours after surgery.
3. To evaluate whether gabapentin enacarbil will decrease length of stay in the hospital. Duration of hospital length of stay in days will be calculated.
4. To evaluate whether gabapentin enacarbil will improve patient's satisfaction. Patient satisfaction will be performed by Outcomes Research Department personnel by using the QoR-15 satisfaction score.

4. SUBJECT SELECTION AND WITHDRAWAL

4.1 Inclusion Criteria

To be eligible for entry into this study, candidates must meet all of the following eligibility criteria at the time of randomization:

1. Men or women 18-85 years of age.
2. Scheduled for elective knee or hip arthroplasty with spinal anesthesia.

4.2 Exclusion Criteria

Candidates will be excluded from study entry if any of the following exclusion criteria exist at the time of randomization.

1. Creatinine >1.50 mg/dl.
2. History of clinically important current depression or currently on any prescribed anti-depressant medication.
3. Previously enrolled in any Xenoport trial.
4. Use of gabapentin or gabapentinoids (Lyrica, Horizant, Neurontin or Gralise) within one month.
5. Allergy to gabapentin or gabapentinoids (Lyrica, Horizant, Neurontin or Gralise).
6. Women who are pregnant or breastfeeding.

7. History of seizure disorder within the last one-year or taking medications for seizures.

4.3 Subject Recruitment and Screening

Screening visit would be within a month before surgery at the pre-operative clinical evaluation visit. Patients will be screened using inclusion and exclusion criteria. The study will be explained to the patients in detail. Participating centers are required to document all screened candidates initially considered for inclusion in this study and to specifically state the reason(s) for their exclusion. A screening log will be maintained in REDCap, which is a Cleveland Clinic internal database system. All screened candidates will be documented for inclusion and also reasons for exclusions from the study.

4.4 Early Withdrawal of Subjects

Patients will be free to withdraw from study at any time. Subjects must be withdrawn from the study for the following reasons:

1. Voluntary withdrawal
2. Adverse event or serious adverse event deemed necessary by investigator for patient safety.
3. Unable to take medication for three post-operative days

4.5 Data Collection and Follow Up for Withdrawn Subjects

1. Data obtained from electronic medical records will include: operation time, surgery type, intraoperative opioid consumption, postoperative opioid consumption in PACU and in ward, breakthrough pain medication requirements, pain scores in PACU and ward, requirement of antiemetics for nausea and vomiting, requirement of antihistaminic medications, requirement of laxatives for constipation, ambulation time, flatus, ileus, bowel movements, length of stay and any side effects or complications.
2. Preoperative and postoperative laboratory data including but not limited to renal function results will also be collected from electronic medical records. Patient functionality will also be recorded including, bathing, toileting, walking and moving.
3. Patients will be evaluated for pain (using numerical rating scale) (NRS) once in the PACU (Post-Anesthesia Care unit) every 15 minutes during the initial first hour after surgery and then on the first, second and third post-operative morning. Amount of opioids used, rescue anti-emetics used, nausea, vomiting and pain scores will be documented in EPIC.
4. With all study patients, post-operative pain at rest will be collected and reflected using the Numerical rating scale (NRS) pain scale. The patient is asked to rate the pain within (0-10), with zero indicating no pain and 10 indicating the worst imaginable pain.
5. Pain will be evaluated both at rest and after exercise as per physiotherapy protocol. This would be a global assessment of pain since the last assessment.
6. Patient satisfaction with their pain treatment will be questioned after 72 hours or at discharge whichever comes first using 0-5 scales and we will also use QoR-15 score to formally evaluate quality of recovery. The QoR-15 score is a validated scoring system allows quantification of patient's early postoperative health status, which is also a

description of quality of recovery. The QoR-15 score will be performed on 72 hours post op or at discharge whichever comes first.

7. Patients will be contacted by telephone at 3 months after surgery and queried regarding presence of new pain since surgery and its interference with activities of daily living. Phone call is made with the purpose of checking for pain conversion from acute to chronic and to check for any adverse event.

5. STUDY DRUG (or Device, Biologic, Treatment)

5.1 Description

Gabapentin is an analog of gamma-aminobutyric acid. It is currently approved by the US Food and Drug Administration for treatment for post herpetic neuralgia and seizure disorders. It binds to alpha-2 delta subunit of presynaptic P/Q voltage gated calcium channels, which regulate the release of excitatory neurotransmitters from nociceptive receptors. We would like to test an extended-release formulation of gabapentin enacarbil, a prodrug of gabapentin. GEN provides more sustained dose proportional exposure to gabapentin (unlike gabapentin), which may lead to more predictable exposure with GEN and decreased dosing frequency relative to gabapentin. Due to the mechanism of action of GEN and its predictable bioavailability due to its absorption via the MCT-11 transporters, we would like to prefer GEN to gabapentin.

5.2 Treatment Regimen

Gabapentin enacarbil 600 mg or placebo will be administered orally one day pre-operatively 12 hours apart with meals and 600 mg gabapentin enacarbil or placebo dose 2 hours before the surgery with sips of water. Post-operative dose of 600 mg gabapentin enacarbil or placebo should be resumed within 6 hours of completion of procedure with sips of water. Patient will receive 600 mg gabapentin enacarbil or placebo doses three additional days postoperatively 12 hours apart with meals.

5.3 Method for Assigning Subjects to Treatment Regimen

Participating patients will be randomly assigned to gabapentin enacarbil or placebo. Randomization will be web-based through REDCap and stratified by type of surgery. Allocation will be concealed until shortly before drug/placebo administration. Randomization will be stratified by type of surgery (hip versus knee). Randomization codes will be web based using random-sized blocks, and treatment assignment (gabapentin enacarbil or placebo) will be done using a password-protected website administered by the Department of Outcomes Research statistical team at Cleveland Clinic.

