GA	=	general anesthesia
POD	=	postoperative day
PACU	=	post anesthesia care unit
EPIC	=	electronic privacy information center
REDCap	=	Research Electronic Data Capture (Cleveland clinic internal database)
PCA	=	Patient controlled Analgesia
NRS	=	Numerical rating scale
GEn	=	Gabapentin enacarbil

CONTENTS

[figure not shown]
Word did not find any entries for your table of contents.

[figure not shown]
In your document, select the words to include in the table of contents, and then on the Home tab, under Styles, click a heading style. Repeat for each heading that you want to include, and then insert the table of contents in your document. To manually create a table of contents, on the Document Elements tab, under Table of Contents, point to a style and then click the down arrow button. Click one of the styles under Manual Table of Contents, and then type the entries manually.

RESEARCH SCHEMA

Title	A randomized controlled trial to determine the effect of gabapentin enacarbil on opioid consumption and pain scores in patients having hip and knee arthroplasties with spinal anesthesia
Short Title	PAIN ATTENUATION IN SURGICAL PATIENTS
Principal Investigator	[name]
Primary Objectives	To assess whether gabapentin enacarbil decreases pain and/or opioid requirements after hip or knee surgery
Secondary Objectives	- To assess whether gabapentin enacarbil decreases the incidence of persistent incisional pain three months after surgery when used as a modality of pre-emptive analgesia. - To evaluate whether gabapentin enacarbil decreases nausea and vomiting during the initial 72 post-operative hours. - To evaluate whether gabapentin enacarbil reduces the duration of hospitalization. - To evaluate whether gabapentin enacarbil improves patient's satisfaction
Study Design	A randomized, double-blind, placebo-controlled, single institution trial
Inclusion Criteria	1. Men or women 18-85 years of age. 2. Scheduled for elective total primary knee or total primary hip arthroplasty with spinal anesthesia.

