5.4 Preparation and Administration of Study Treatment

Xenoport will supply Cleveland Clinic Fairview hospital and Cleveland Clinic Main Campus pharmacy with gabapentin enacarbil and identically looking placebo. Gabapentin enacarbil

or placebo will be administered orally with meals a day before the surgery, with sips of water pre-operatively and again with meals post-operatively. Both gabapentin enacarbil and placebo will have an identical package, with regards to appearance and physical properties. They will both be administered as oral tablets with sips of water or meals.

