5.9.3 Dispensing of Study Drug

Cleveland Clinic Fairview hospital and Cleveland Clinic Main Campus will maintain accurate records demonstrating dates and amount of study drug received, to whom they are dispensed (subject-by-subject accounting), and accounts of any study drug accidentally or deliberately destroyed.

Study drug reconciliation will be performed to document drug assigned, drug consumed, and drug remaining. This reconciliation will be logged on the reconciliation form, and signed and dated by the study team.

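### Two hospitals dispense study drug, but hospital is neither a stratification factor nor a term in the primary models; the cost is some precision on the opioid comparison, not bias

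*Combined protocol and SAP*

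**What the plan says.** The research schema describes "A randomized, double-blind, placebo-controlled, single institution trial". Section 5.4 has the drug company supplying the pharmacies of two Cleveland Clinic hospitals, and 5.9.1, 5.9.3 and 5.9.4 repeat both names for receipt, dispensing and return. Section 5.9.3 reads "Cleveland Clinic Fairview hospital and Cleveland Clinic Main Campus will maintain accurate records demonstrating dates and amount of study drug received", with accounting subject by subject. Section 4.3 uses the plural: "Participating centers are required to document all screened candidates initially considered for inclusion in this study".

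On allocation, 5.3 says "Randomization will be stratified by type of surgery (hip versus knee"; 3.1 agrees, and hospital is not mentioned.

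On background care, 3.1 gives both arms standard management without defining it, and 5.8 leaves clinicians to their usual postoperative care. Section 5.6 bars gabapentinoids and then says "All other pain medications will be allowed". Section 3.2 lists "morphine PCA, fentanyl PCA or hydromorphone PCA" without a rule for choosing among them.

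On analysis, 7.2 plans a log-linear regression for opioid consumption and a linear regression for time-weighted pain. It names no covariates for either and checks baseline balance descriptively.

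**The concern.** Nothing in the plan holds analgesic practice constant across the two hospitals, so opioid totals may plausibly differ between them. The plan also gives no discharge criteria, and opioid counting stops at 72 hours or discharge, so the collection window may differ too. If so, hospital explains part of the outcome variance, and a model that omits it leaves that part in the standard error.

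Noninferiority on opioids is required for any positive conclusion under 7.2, and the margin is a ratio of only 1.1. Precision matters most if the drug wins on pain alone. If it wins on opioids, with the upper limit of the 97.5% interval below 1, noninferiority on opioids follows automatically.

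**Working it through.** **Inputs from the documents.** 50 per arm, CV 0.7, ratio 0.63, significance level 0.0125, about 90% power (7.1); 1-tailed tests, margin 1.1, upper 95% limit rule (7.2).

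**Plan's own figure.** Log SD = sqrt(ln(1 + 0.7²)) = 0.6315. SE of the log ratio = 0.6315 × sqrt(2/50) = 0.1263. The effect is |ln 0.63| = 0.4620. A one-sided t-test at 0.0125 with 98 df has 91.5% power, which agrees with the stated figure of about 90%.

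**How tight the opioid margin is.** ln 1.1 = 0.0953, already smaller than the SE. The upper limit falls below 1.1 only if the observed ratio is below exp(0.0953 − 1.984 × 0.1263) = 0.856. Noninferiority power is about 11% at a true ratio of 1.0, 70% at 0.8 and 99% at 0.63.

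**Assumptions not in the documents.** The ratio r of geometric mean opioid use between hospitals, and the share p of patients at one hospital. I take p = 0.5 and let r run from 1.1 to 2.0, with the total log SD held at 0.6315.

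**Formulas.**
- Hospital share of log variance = p(1 − p)(ln r)² / 0.3988.
- SE with the hospital term = 0.1263 × sqrt(1 − share).
- SD of the chance difference in hospital mix between arms = sqrt(p(1 − p) × 2/50) = 0.10 at p = 0.5 and 0.092 at p = 0.7.
- Shift from a 2 SD imbalance = exp(2 × SD × ln r).

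| r | Variance share | SE with term | SE reduction | 2 SD shift, 50:50 | 2 SD shift, 70:30 |
|---|---|---|---|---|---|
| 1.1 | 0.6% | 0.1259 | 0.3% | 1.9% | 1.8% |
| 1.2 | 2.1% | 0.1250 | 1.0% | 3.7% | 3.4% |
| 1.3 | 4.3% | 0.1235 | 2.2% | 5.4% | 4.9% |
| 1.5 | 10.3% | 0.1196 | 5.3% | 8.4% | 7.7% |
| 2.0 | 30.1% | 0.1056 | 16.4% | 14.9% | 13.5% |

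The last two columns apply to the unadjusted ratio. In sample-size terms, the term is worth 100/(1 − share): about 102 patients' information from 100 at r = 1.2, 111 at 1.5 and 143 at 2.0.

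**If the CV of 0.7 is a within-hospital figure** (the plan does not say), the unadjusted SE is 0.2 × sqrt(0.3988 + 0.25(ln r)²), and adjustment brings it back to 0.1263. The reductions are then 1.0%, 2.1%, 4.8% and 12.3% for r = 1.2, 1.3, 1.5 and 2.0, much the same.

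**Simulation.** 6,000 trials per setting, 50:50 split, random blocks (sizes 2, 4 and 6 assumed) within joint, hospital not stratified:

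| r | Type I error at true ratio 1.1, unadjusted | Same, adjusted | Noninferiority power at true ratio 0.8, unadjusted | Same, adjusted |
|---|---|---|---|---|
| 1.2 | 2.8% | 2.7% | 71% | 71% |
| 1.5 | 2.1% | 2.2% | 71% | 75% |
| 2.0 | 2.0% | 2.3% | 71% | 85% |

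**What stratification adds once the model adjusts.** With p = 0.5, a difference d in hospital share multiplies the variance of the adjusted estimate by 1/(1 − d²). For a typical d of 0.10 this is 1.010, or 0.5% in SE; for d = 0.20 it is 1.042, or about 2% in SE. Nearly all of the gain comes from the model term.

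No SD for the pain score is given, so the gain on that outcome cannot be sized.

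**The case against.** The strongest reply is that chance imbalance under valid randomisation is ordinary sampling error, which the confidence interval already covers. That stands: simulated type I error without a hospital term was 2.0% to 2.8% against a nominal 2.5%.

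A reader might infer from the shifts in the table that a hospital imbalance could consume most of the 10% margin. The documents do not support that as a general statement. It needs hospitals that differ by about 1.5 or more together with an imbalance near 2 SD, which has about a 2.3% chance in a given direction. The probability of an unfavourable shift larger than half the log margin is 0.5% at r = 1.2, 3.5% at 1.3, 12% at 1.5 and 25% at 2.0, and no document says where r lies. Nor is the margin the right yardstick, because the decision rests on the upper confidence limit. Against the SE, the 2 SD shift at r = 1.5 is 0.20 × 0.4055 / 0.1263 = 0.64.

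A reader might also call the single-institution label false. Both hospitals belong to Cleveland Clinic, so it is ambiguous rather than wrong. It does leave a reader of the schema unaware of the second hospital.

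Finally, a hospital effect is plausible but not documented. The plan does limit some variation: gabapentinoids are barred, opioids are converted to morphine equivalents, and outcome evaluators are blinded. If practice is similar at both hospitals, the term gains almost nothing, but it also costs almost nothing.

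**Conclusion.** The omission is real, and its consequence is a possible loss of precision. The unadjusted analysis remains valid. Under a 50:50 split and a total log SD of 0.63, the opioid SE would fall by about 1% at a hospital ratio of 1.2, 2% at 1.3, 5% at 1.5 and 16% at 2.0; noninferiority power at a true ratio of 0.8 would stay at about 71% for 1.2 and rise to 75% at 1.5 or 85% at 2.0. The hospital ratio and the split are assumptions throughout. The larger difficulty is ordinary sampling error against a narrow margin, which a hospital term eases only in part. That scarcity is still a good reason to take a near-free gain.

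**What to change.** - **7.2:** prespecify hospital (two levels) as a covariate in both primary regressions, opioid and pain. This carries nearly all of the benefit.
- **5.3:** if enrolment has not started, stratify the REDCap randomisation by hospital as well as joint, giving four strata with the same random-sized blocks. This adds little beyond the covariate. If enrolment has started, keep the existing list and add only the model term, before outcomes are examined by treatment group.
- **Research schema:** describe the trial as one institution with two hospitals.

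The cost is one degree of freedom, one randomisation setting and slightly more incomplete blocks. No additional patients are needed, and 5.9.3 already has each hospital account for drug subject by subject, so the hospital of each patient will be known.
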